8.2.6 Fatal Outcome

Any SAE that results in the subject’s death (ie, the SAE was noted as the primary cause of death) must have fatal checked as an outcome with the date of death recorded as the resolution date. For all other events ongoing at the time of death that did not contribute to the subject’s death, the outcome should be considered not resolved, without a resolution date recorded.

For any SAE that results in the subject’s death or any ongoing events at the time of death, unless another investigational product action was previously taken (eg, drug interrupted, reduced, withdrawn), the action taken with the investigational product should be recorded as “dose not changed” or “not applicable” (if the subject never received investigational product). The investigational product action of withdrawn should not be selected solely as a result of the subject’s death.

8.2.7 Regulatory Agency, Institutional Review Board, and Site Reporting

The sponsor is responsible for notifying the relevant regulatory authorities/United States (US) central IRBs of related, unexpected SAEs.

In addition the sponsor is responsible for notifying active sites of all related, unexpected SAEs occurring during all interventional studies across the SHP639 program.

The investigator is responsible for notifying the local IRB or the relevant local regulatory authority of all SAEs that occur at his/her site as required.

9. DATA MANAGEMENT AND STATISTICAL METHODS

9.1 Data Collection

The investigators' authorized site personnel must enter the information required by the protocol on the eCRF. A study monitor will visit each site in accordance with the monitoring plan and review the eCRF data against the source data for completeness and accuracy. Discrepancies between source data and data entered on the eCRF will be addressed by qualified site personnel. When a data discrepancy warrants correction, the correction will be made by authorized site personnel. Data collection procedures will be discussed with the site at the site initiation visit and/or at the investigator's meeting. Once a subject is randomly assigned, it is expected that site personnel will complete the eCRF entry within approximately 3 business days of the subject's visit.

9.2 Clinical Data Management

Data are to be entered into a clinical database as specified in the CRO's data management plan. Quality control and data validation procedures are applied to ensure the validity and accuracy of the clinical database.

Data are to be reviewed and checked for omissions, errors, and values requiring further clarification using computerized and manual procedures. Data queries requiring clarification are to be communicated to the site for resolution. Only authorized personnel will make corrections to the clinical database, and all corrections are documented in an auditable manner.

9.3 Data Handling Considerations

Data that may potentially unmask the treatment assignment (ie, investigational product blood concentrations, antidrug antibody, treatment allocation, and investigational product preparation/accountability data) will be handled with special care during the data cleaning and review process. These data will be handled in such a way that, before unmasking, any data that may unmask study team personnel will be presented as masked information or otherwise will not be made available. If applicable, unmasked data may be made available to quality assurance representatives for the purposes of conducting independent drug audits.

9.4 Statistical Analysis Process

The study will be analyzed by the sponsor or its agent.

The statistical analysis plan (SAP) will provide the statistical methods and definitions for the analysis of the PK, PD, and safety data, as well as describe the approaches to be taken for summarizing other study information such as subject disposition, demographics and baseline characteristics, investigational product exposure, and prior and concomitant medications. The SAP will also include a description of how missing, unused and spurious data will be addressed.

To preserve the integrity of the statistical analysis and study conclusions, the SAP will be finalized before database lock.

All statistical analyses will be performed using SAS[®] software (SAS Institute, Inc, Cary, NC 27513).

9.5 Planned Interim Analysis, Adaptive Design, and Dose Escalation Committee

Shire's Dose Escalation Committee will be convened consisting of the coordinating principal ophthalmologist and Shire medical monitor. Ad hoc study team members can be included such as biostatistics, pharmacokinetics, drug safety, and clinical operations if needed. The committee will review collective safety data for Cohort A and Cohort B to decide whether Part 2 in the same dose level and Part 1 in the next dose level (concentration) can commence.

An unmasked interim analysis (IA) will be performed after cohorts A1, A2, A3, B1, B2, and B3 have completed through Day 29 of the B3 cohort. Data from sites will be entered into the database, queried, and discrepancies resolved. There is no intention to stop early based on data from the IA. The intent of this IA is to determine if the escalated doses have identified a pharmacodynamically significant safe and tolerable dose(s) for further clinical evaluation.

Team members reviewing the interim analysis will be reviewing unmasked data from cohorts A1, A2, A3, B1, B2, and B3. The SAP will be finalized before data are frozen for this interim analysis.

All cohorts conducted after B3 (ie Part 1 of the study) may be unmasked following completion of Day 29 to permit review of safety, tolerability and the pharmacodynamics effects of each cohort to better inform planning for additional cohorts and further clinical development options for SHP639.

A final unmasked analysis will be conducted when all subjects of the remaining cohorts have completed through Day 29. The Day 88/FU visit is the planned study completion for each subject.

9.6 Sample Size Calculation and Power Considerations

A sufficient number of subjects will be screened to ensure the enrollment and completion of 84 subjects.

The number of subjects in this study is not based on statistical power considerations because the statistical analyses are primarily descriptive in nature. However, if at least 7 subjects complete each cohort, then there will be at least 65% to 85% probability of observing at least 1 occurrence of any AE with a true incidence rate for a given dose group of at least 15-25%, respectively.

It is estimated that dose escalation will occur for up to 3 dose levels (4 cohorts within each dose level). Each cohort will include 5 subjects randomized to active drug and 2 subjects randomized to placebo for an estimated total of at least 84 subjects.

For each cohort, the number of subjects will be increased as needed based on safety and IOP response. Any cohort can be repeated to confirm findings with regard to safety or IOP response.

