Title of the study: A Randomized, Double-masked, Placebo-controlled Phase 1 Study to Assess the Safety, Tolerability, Pharmacokinetics, and Pharmacodynamics of Single Daily and Multiple Daily Ascending Doses of SHP639 Topical Ophthalmic Solution in Subjects with Ocular Hypertension or Primary Open-angle Glaucoma (POAG).	
Number of subjects (total and for each treatment arm): Approximately 120 subjects will be screened to ensure the enrollment and completion of 84 subjects. There will be approximately 12 cohorts, each consisting of 7 subjects. Subjects may be replaced to ensure 6 out of 7 completers per dosing regimen cohort.	
Investigator(s): [name] (coordinating principal ophthalmologist)	
Site(s) and Region(s): This is a multicenter study conducted solely in the United States. Approximately 7 sites will participate in the study.	
Study period (planned): 2017 to 2018	Clinical phase: 1
Objectives: Primary: To investigate the safety and tolerability of single and multiple ascending doses of SHP639 ophthalmic solution in subjects with ocular hypertension (OHT) or with primary open-angle glaucoma (POAG). Secondary: To evaluate reduction of intraocular pressure (IOP), as a pharmacodynamic (PD) biomarker, following different SHP639 dosing regimens. Exploratory: To explore the pharmacokinetic (PK)-PD relationship of SHP639 in subjects with OHT or POAG	
Rationale: SHP639 is being developed for reduction of IOP in glaucoma patients. It is expected to act through a novel mode of action (natriuretic peptide receptor B agonism) that leads to an increase in trabecular meshwork outflow, thus reducing the IOP. SHP639-101 is a first-in-human clinical study for a topical ophthalmic formulation of SHP639. Up to 3 different concentrations (0.1%, 0.3%, and 0.6%) will be explored and safety and tolerability of SHP639 ophthalmic solution will be evaluated. As a secondary objective, the study will also aim to characterize the PD of SHP639, using IOP as a PD biomarker. The PK-PD relationship will be explored if the data permit.	
Investigational product, dose, and mode of administration: Topical ophthalmic drops of 3 SHP639 concentrations and matching placebo will be used in this study: 0.1%, 0.3%, and 0.6%. Each concentration will be given in an ascending dose fashion once daily (QD), twice daily (BID), 3 times daily (TID), and 4 times daily (QID).	

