3. STUDY DESIGN

3.1 Study Design and Flow Chart

This is a multicenter, randomized, double-masked, placebo-controlled, single- and multiple-dose escalation study. Three different SHP639 concentrations will be studied: 0.1%, 0.3%, and 0.6%. There will be up to 12 cohorts in total, 1 cohort for each dose level and different dosing regimen. Each cohort will consist of 7 subjects for a total of 84 subjects in the study. Eligible subjects will be randomized in a 5:2 ratio to receive either SHP639 or placebo, respectively. The anticipated doses being studied for each dosing regimen are presented in the dose-escalation scheme in [Table 10](#).

A sufficient number of subjects will be screened and enrolled to ensure that at least 6 of 7 subjects complete each treatment in their assigned cohort. In the event that a sufficient number of subjects do not complete a cohort, replacement subjects may be enrolled. Each replacement subject will follow the same screening procedures and randomization sequence as the subject who is discontinued, regardless of when the subject discontinued.

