6.2.3.2 Dose Escalation

Throughout the study, dose escalation meetings will commence at regular time points to review safety data and authorize progression into the next cohort. The anticipated dose escalation scheme is presented in Table 10.

- Single-dose cohorts: a dose escalation meeting may convene after a minimum of 6 subjects have completed the 24-hour assessments for the SDTP. At the dose escalation meeting, a preselected Dose Escalation Committee will determine whether it is safe to continue to the anticipated cohort at either the next dose level or the next dosing regimen.
- Multiple-dose cohorts: a dose escalation meeting may convene after a minimum of 6 subjects have completed the Day 14 assessments for the MDTP. At the dose escalation meeting, a preselected Dose Escalation Committee will determine whether it is safe to continue to the anticipated cohort at either the next dose level or the next dosing regimen. If the dose escalation meeting was held prior to the completion of the cohort, the remainder of the treatment period will be completed following the dose escalation meeting.

Table 10 Anticipated Dose-escalation Scheme

Dose Authorized by Committee			Enabling Required Dose-escalation Activity					
			Before Switch from Single to Multiple Dose - BID, TID, or QID			Before Increasing Dose Level		
Cohort	Dose	Regimen	Cohort	Dose	Regimen	Cohort	Dose	Regimen
A1	0.1%/Placebo	SD	NA	–	–	NA	–	–
A1	0.1%/Placebo	QD	A1	0.1%/Placebo	SD	NA	–	–
A2	0.3%/Placebo	SD	NA	–	–	A1	0.1%/Placebo	SD
A2	0.3%/Placebo	QD	A2	0.3%/Placebo	SD	A1	0.1%/Placebo	QD
A3	0.6%/Placebo	SD	NA	–	–	A2	0.3%/Placebo	SD
A3	0.6%/Placebo	QD	A3	0.6%/Placebo	SD	A2	0.3%/Placebo	QD
B1	0.1%/Placebo	BID	A1	0.1%/Placebo	QD	NA	/–	–
B2	0.3%/Placebo	BID	A2	0.3%/Placebo	QD	B1	0.1%/Placebo	BID
B3	0.6%/Placebo	BID	A3	0.6%/Placebo	QD	B2	0.3%/Placebo	BID
C1	0.1%/Placebo	TID	B1	0.1%/Placebo	BID	NA	/–	–
C2	0.3%/Placebo	TID	B2	0.3%/Placebo	BID	C1	0.1%/Placebo	TID
C3	0.6%/Placebo	TID	B3	0.6%/Placebo	BID	C2	0.3%/Placebo	TID
D1 ^a	0.1%/Placebo	QID	C1	0.1%/Placebo	TID	NA	–/	–
D2	0.3%/Placebo	QID	C2	0.3%/Placebo	TID	D1	0.1%/Placebo	QID
D3	0.6%/Placebo	QID	C3	0.6%/Placebo	TID	D2	0.3%/Placebo	QID

BID=twice daily; NA= not applicable; QD=once daily; QID=4 times daily; SD=single dose; TID=3 times daily.

^a Cohort D1 is not to be enrolled as it was decided that the resulting data would not contribute to the understanding of the safety of SHP639.

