2.3 Determination of Sample Size

A sufficient number of subjects will be screened to ensure the enrollment and completion of 84 subjects.

The number of subjects in this study is not based on statistical power considerations because the statistical analyses are primarily descriptive in nature. However, if at least 7 subjects complete each cohort, then there will be at least 65% to 85% probability of observing at least 1 occurrence of any AE with a true incidence rate for a given dose group of at least 15% to 25%, respectively.

It is estimated that dose escalation will occur for up to 3 dose levels (4 cohorts within each dose level). Each cohort will include 5 subjects randomized to active drug (SHP639) and 2 subjects randomized to placebo for an estimated total of at least 84 subjects.

For each cohort, the number of subjects will be increased as needed based on safety and IOP response to investigational product. Any cohort can be repeated to confirm findings with regard to safety or IOP response to investigational product.

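### The plan commits to 84 completers, but its own rule targets 6 of 7 per cohort; the 84 was not updated for cancelled D1 or the B3 repeat, and the AE-detection figure counts placebo subjects

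*Protocol*

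**What the plan says.** Protocol 9.6 and SAP 2.3 give the size in the same words: "A sufficient number of subjects will be screened to ensure the enrollment and completion of 84 subjects". The synopsis adds the screening number: "Approximately 120 subjects will be screened to ensure the enrollment and completion of 84 subjects".

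The design behind the figure is in Protocol 3.1: "There will be up to 12 cohorts in total, 1 cohort for each dose level and different dosing regimen", with 7 subjects in each. Protocol 9.6 gives the split: "Each cohort will include 5 subjects randomized to active drug and 2 subjects randomized to placebo". The completion rule, also in 3.1, is that enough subjects will be enrolled "to ensure that at least 6 of 7 subjects complete each treatment in their assigned cohort". Section 4.5 makes replacement discretionary for the sponsor and sets the same 6-of-7 target. The synopsis states that target in the same entry as the 84 completers.

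Two later decisions bear on the count. Footnote a to Table 10 (Protocol 6.2.3.2) says "Cohort D1 is not to be enrolled", and the synopsis carries a similar footnote. SAP 13 reports that Cohort B3 was repeated and that an interim analysis of the repeat was done in June 2018. Its size is not stated.

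The only numerical support for the cohort size is a detection statement in Protocol 9.6, the synopsis and SAP 2.3. It opens "However, if at least 7 subjects complete each cohort" and gives at least 65% to 85% probability of seeing one or more occurrences of an AE whose true incidence in a given dose group is at least 15% to 25%.

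**The concern.** A commitment to 84 completers and a rule that accepts 6 of 7 per cohort cannot both describe the same study. The 84 and the count of four cohorts per dose level also stand unchanged after D1 was dropped, although the 0.1% level now has three listed cohorts (A1, B1, C1). The SAP repeats the 84 while reporting the B3 repeat elsewhere.

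What is at stake is the accuracy of the stated size and of its one quantitative justification. This is a first-in-human study whose primary objective is safety and tolerability. A reader who relies on the sample size section would expect more completers than the rules aim for, and a better chance of seeing an AE at a given dose and regimen than five active subjects provide.

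**Working it through.** **Inputs.** Three concentrations and four regimens (Protocol 3.1, Table 10); 5 active + 2 placebo per cohort (9.6); target of at least 6 of 7 completers (3.1, 4.5); D1 not enrolled (Table 10, footnote a); B3 repeated (SAP 13), size not given and taken here as 7 by assumption.

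**Reproducing the stated size.** 3 × 4 × (5 + 2) = 12 × 7 = 84. The enrollment figure reproduces for 12 cohorts of 7. As a completer figure it needs 7 of 7 in all 12.

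**Completers under the 6-of-7 rule.** Planned enrollment = cohorts × 7; target minimum completers = cohorts × 6. Replacements and enlargements are excluded.

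| Cohorts counted | Planned enrolled | Active / placebo | Target minimum completers |
|---|---|---|---|
| 12 as first planned | 12 × 7 = 84 | 60 / 24 | 12 × 6 = 72 |
| 11 listed, without D1 | 11 × 7 = 77 | 55 / 22 | 11 × 6 = 66 |
| 11 listed + B3 repeat (7 assumed) | 12 × 7 = 84 | 60 / 24 | 12 × 6 = 72 |

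No row has a target of 84 completers.

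**Reproducing the detection statement.** With independent subjects, P(at least one event) = 1 − (1 − p)^n.

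- n = 7: 1 − 0.85^7 = 67.9% at 15%; 1 − 0.75^7 = 86.7% at 25%. This meets the stated 65% and 85%.
- n = 6: 62.3% and 82.2%. This meets neither, so 7 is the smallest n that supports the statement.

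Seven is the whole cohort, including its 2 placebo subjects. They carry no information on an AE rate under active treatment, and the safety analysis places them in pooled placebo groups (Protocol 9.9.2; SAP 4.3 and 11).

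**Detection with the active subjects.**

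- n = 5: 1 − 0.85^5 = 55.6% at 15%; 1 − 0.75^5 = 76.3% at 25%.

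The chance of seeing no such event at 15% incidence is therefore 44.4%, against 32.1% with n = 7 and at most 35% as stated. At 25% it is 23.7%, against 13.3% with n = 7 and at most 15% as stated.

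**The case against.** The documents hedge. Protocol 9.6 calls its total an estimate and a lower bound, the number of cohorts is a maximum, cohorts may be enlarged or repeated, and the D1 decision is disclosed in footnotes. The size is expressly not power-based and the analyses are primarily descriptive, so no test, analysis set or escalation rule depends on the 84. The detection sentence is conditional on 7 completers, and under that condition its arithmetic is right. If the B3 repeat had 7 subjects, the enrollment half of the 84 is right as well.

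Most of this stands, and it limits the consequence. It does not remove the conflict. Enlargement and repetition depend on safety and IOP response, and neither requires 7 of 7 completers. The condition in the detection sentence is one the plan does not aim to meet, and meeting it would still leave 2 of the 7 on placebo.

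Two stronger readings are tempting, and the documents do not support them.

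- A reader might infer that the rules guarantee 66 completers out of 77 enrolled. Nothing fixes either number. Replacement is at the sponsor's discretion, and each replacement raises enrollment. Further cohorts may be judged unnecessary (6.2.3.2), and others may be enlarged or repeated, as B3 was.
- A reader might infer that losing one active subject leaves 4, so detection falls to 47.8% at 15% and 68.4% at 25%. That counts completers. AEs are analysed in everyone randomized and dosed (Protocol 9.7; SAP 4.3), so a dropout's events still count, although that subject is observed for a shorter time. The basis is 5 active subjects dosed, whether or not all complete.

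**Conclusion.** The stated 84 completers does not follow from the plan's own rules. The rule targets at least 72 for 12 cohorts. For the 11 listed cohorts it targets at least 66 of 77 planned, before replacements, enlargements or repeats. With the B3 repeat the figures are 84 planned and at least 72, assuming 7 subjects in the repeat. These are targets, not assured results.

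The 65% to 85% detection claim is correct for 7 subjects but overstates what one cohort shows about active treatment: 55.6% and 76.3% with 5 active. This takes a dose group to be the active arm of one cohort, because the sentence conditions on completers in each cohort, and it treats subjects as independent.

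This should be corrected, but the effect is on the stated size and its justification; no hypothesis test or power figure is affected.

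**What to change.** In Protocol 9.6, the synopsis and SAP 2.3, replace the commitment to 84 completers with two statements: planned enrollment for the cohorts actually to be run (the 11 listed cohorts, 77 subjects, plus any repeat at its actual size), and a target of at least 6 of 7 completers per cohort. Correct the four-cohorts-per-dose-level count for D1, and bring the total of 84 in Protocol 3.1 and SAP 2.1 into line.

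Restate AE detection on the 5 active subjects dosed per cohort: 55.6% at 15% incidence and 76.3% at 25%. Do not tie it to completers, since the safety set is all dosed subjects.

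The cost is wording in the protocol and SAP. No subjects are added and conduct does not change. The downside is that the published figures look less favourable.

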Plasma concentrations of SHP639 will be measured using a fully validated bioanalytical method. If data permit, PK parameters for SHP639 will be calculated based on plasma concentration-time data using a noncompartmental approach). Pharmacokinetic parameters may include, but are not limited to, the following: maximum observed concentration (C_{max}); time to reach C_{max} (t_{max}); area under the observed concentration vs time curve from time zero (predose) to the time of the last measurable concentration (AUC_{0-t}), over the dosing interval ($AUC_{0-\tau}$) for each multiple-dose regimen, and from time zero (predose) extrapolated to infinity ($AUC_{0-\infty}$); apparent terminal phase elimination half-life ($t_{1/2}$); apparent clearance (CL/F); apparent volume of distribution (V_z/F); and accumulation ratios based on AUC and C_{max} for each multiple-dose regimen.

Pharmacodynamic Endpoints

Intraocular pressure (IOP; mmHg) will be measured using Goldmann applanation tonometry. Pharmacodynamic parameters will be estimated as appropriate and may include, but are not limited to, the following: change from baseline in IOP; time to the maximum change from baseline in IOP; and proportion of subjects maintaining IOP reduction after specified days of treatment.

Specific endpoints in order to understand the effect of SHP639 on IOP will be defined in the SAP.

Safety Endpoints

Safety and tolerability will be assessed by monitoring AEs, vital sign measurements, clinical laboratory assays, electrocardiogram (ECG), ADA, drop comfort assessment, and ophthalmologic examinations.

Sample Size Justification

The number of subjects in this study is not based on statistical power considerations because the statistical analyses are primarily descriptive in nature. However, if at least 7 subjects complete each cohort, then there will be at least 65- 85% probability of observing at least 1 occurrence of any AE with a true incidence rate for a given dose group of at least 15- 25%, respectively.

It is estimated that dose escalation will occur for up to 3 dose levels (4 cohorts within each dose level). Each cohort will include 5 subjects randomized to active drug and 2 subjects randomized to placebo for an estimated total of at least 84 subjects.

For each cohort, the number of subjects will be increased as needed based on safety and IOP response. Any cohort can be repeated to confirm findings with regard to safety or IOP response.

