4.5.4 Stopping Criteria for Dose Escalation

1. Progressing from a dosing regimen cohort to the next or from a study part to the next will not occur in the presence of moderate or severe drug-related ocular AEs in 2 or more SHP639-treated subjects in a given cohort.
2. If 1 or more subjects experience corneal hazing of grade 3 or greater on the Hwang Grading Scale of Corneal Haze, they will be discontinued from the study. At that time, the study will stop for further evaluation by the Shire's Dose Escalation Committee.

3. If 2 or more subjects in a given cohort receiving active drug have a severe AE in the same organ or body system, no further subjects will be enrolled or dosed until further evaluation of the available data is made by the medical monitor and investigator to determine whether to stop or proceed with the study. Following a safety review of the event, study enrollment or dosing of currently enrolled subjects may be restarted if the medical monitor and the investigator determine that it is safe to proceed with the study.
4. If any other drug-related event occurs in subjects receiving active drug and is deemed to pose an unacceptable risk to subjects by the investigator or medical monitor after further evaluation, no further subjects will be enrolled or dosed until further evaluation of the available data is made by the medical monitor and investigator to determine whether to stop or proceed with the study. Following a safety review of the event, study enrollment or dosing of currently enrolled subjects may be restarted if the medical monitor and the investigator determine that it is safe to proceed with the study.

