9.9.2 Statistical Analysis of Safety Data

The placebo subjects will be pooled together as a pooled placebo group.

All vital sign, clinical laboratory, ECG, ADA, drop comfort assessment, and ophthalmologic examination data (per schedule of events) will be listed by dose, cohort, subject, treatment period (single dose or multiple dose; Cohort A only), visit, day, and time point (for days with multiple assessments per day). If the ranges are available then abnormalities will be flagged. Summary statistics with number of subjects, mean, SD, median, minimum, and maximum will be provided by dose, cohort, treatment period (single dose or multiple dose; Cohort A only), visit, day, and time point (for days with multiple assessments per day).

Adverse events will be coded using the Medical Dictionary for Regulatory Activities. The number of events, incidence, and percentage of treatment-emergent AEs will be calculated overall and by system organ class and preferred term by dose and cohort. Treatment-emergent AEs will be further summarized by severity and relationship to investigational product. Adverse events related to investigational product, AEs leading to withdrawal, SAEs, and deaths will be similarly summarized/listed. All information obtained on AEs will be displayed by dose, cohort, subject, treatment period (single dose or multiple dose; Cohort A only), visit, and day. A subject with multiple AEs within a body system will be counted only once.

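### The stated 65% to 85% chance of seeing an adverse event counts all 7 cohort subjects; the 5 on SHP639 give 55.6% to 76.3%

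*Protocol*

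**What the plan says.** Protocol 9.6 explains that the number of subjects does not come from power considerations, because the analyses are mainly descriptive. It then offers one probability statement: "if at least 7 subjects complete each cohort, then there will be at least 65% to 85% probability of observing at least 1 occurrence". The event meant is an AE whose true rate in the dose group concerned is 15% or more for the lower figure and 25% or more for the upper. The synopsis ("there will be at least 65- 85% probability of observing at least 1 occurrence of any AE") and SAP 2.3 ("there will be at least 65% to 85% probability of observing at least 1 occurrence of any AE") repeat it.

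The next paragraph of Protocol 9.6 gives the composition of a cohort: "Each cohort will include 5 subjects randomized to active drug and 2 subjects randomized to placebo".

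Other sections bear on who belongs to a dose group:

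- Protocol 9.9.2 tabulates treatment-emergent AEs by system organ class and "preferred term by dose and cohort", and pools placebo subjects into their own group. SAP 4.3 does the same.
- SAP 11 pools placebo subjects by regimen for ocular summaries in the multiple-dose period.
- The first criterion in Protocol 4.5.4 counts "moderate or severe drug-related ocular AEs in 2 or more SHP639-treated subjects in a given cohort".
- Protocol 3.1 aims only to ensure that "at least 6 of 7 subjects complete each treatment in their assigned cohort".

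**The concern.** The probability concerns an AE rate in a dose group, but its denominator is the whole cohort. Two of the seven subjects never receive the dose whose AE rate is at issue. If they are counted as exposed, the plan overstates what one cohort can reveal about SHP639.

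Safety and tolerability are the primary objective, and this is the only quantitative support given for the cohort size. A reader who relies on it would draw too much reassurance from a cohort in which no events of a given kind are seen among the subjects on active drug.

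**Working it through.** **Inputs.** From Protocol 9.6: 7 subjects per cohort, 5 on SHP639 and 2 on placebo; true incidence p = 0.15 (paired with a floor of 65%) and p = 0.25 (paired with 85%).

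**Formula.** With n independent subjects at common incidence p, the probability of at least one occurrence is 1 − (1 − p)^n.

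**The plan's figure, n = 7.** 1 − 0.85^7 = 67.9% and 1 − 0.75^7 = 86.7%. Both floors hold. Solving for n, ln(0.35)/ln(0.85) = 6.46 and ln(0.15)/ln(0.75) = 6.59, so 7 is the smallest whole number that meets either floor. Within one cohort, the sentence therefore has to count all 7 subjects.

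**Subjects on SHP639, n = 5.** 1 − 0.85^5 = 1 − 0.4437 = 55.6% and 1 − 0.75^5 = 1 − 0.2373 = 76.3%.

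| Subjects counted | p = 15% | p = 25% |
|---|---|---|
| 7 (whole cohort) | 67.9% | 86.7% |
| 6 (minimum completers, whole cohort) | 62.3% | 82.2% |
| 5 (all on SHP639) | 55.6% | 76.3% |
| 4 (one SHP639 subject lost) | 47.8% | 68.4% |
| Stated floor | 65% | 85% |

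**Shortfall at n = 5.** 65 − 55.6 = 9.4 points and 85 − 76.3 = 8.7 points. The chance of missing the AE is 44.4% at p = 15%, where the text implies at most 35%, and 23.7% at p = 25%, where it implies at most 15%.

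**Incidence needed with 5 subjects.** 1 − 0.35^(1/5) = 18.9% for a 65% chance and 1 − 0.15^(1/5) = 31.6% for an 85% chance.

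**Other readings tried.**

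1. *All 7 counted, with the 15% or 25% applying to SHP639 and a placebo rate q.* The probability is 1 − (1 − p)^5 (1 − q)^2. It reaches 65% at p = 15% only if q is at least 11.2%, and 85% at p = 25% only if q is at least 20.5%. No placebo rate is stated, and an AE seen only on active drug stays at 55.6% or 76.3%.
2. *Dose group as one concentration pooled over its four regimens.* That gives 4 × 5 = 20 active subjects (96.1% and 99.7%), or 15 for 0.1% because Cohort D1 is not enrolled (91.3% and 98.7%). These values are far above the stated floors, and the sentence is conditioned on 7 subjects per cohort.
3. *A repeated cohort.* The plan allows this ("Any cohort can be repeated to confirm findings with regard to safety or IOP response"), and SAP 13 records a repeat of B3. If the repeat is the same size, an assumption, there are 10 active subjects (80.3% and 94.4%). That applies to the repeated dose group only, not to the single cohort the sentence describes.

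**The case against.** The strongest reply is that nothing is miscalculated: the floors follow exactly from the sentence's own condition of 7 completers, and dose group is undefined. The dose tables label each cohort as a concentration with placebo, and the sentence says any AE, not a drug-related one. If 15% or 25% is the average rate over the whole cohort, the floors hold for any split between drug and placebo. With no events on placebo and 21% on active drug, the cohort mean is 5 × 21/7 = 15% and the probability is 1 − 0.79^5 = 69.2%. With 35% on active drug, the mean is 25% and the probability is 1 − 0.65^5 = 88.4%.

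That algebra is right. But the rate it uses blends drug and placebo, and so is not the rate in a dose group when AEs are tabulated by dose and placebo is kept apart.

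There are further points. Protocol 6.2.3.2 states the progression rule without restricting it to SHP639-treated subjects. SAP 11 also plans displays combining active and placebo subjects within a regimen. Protocol 9.6 opens with a target of 84 completers, which over 12 cohorts is 7 each. All three are accurate, and the last softens the contrast with the 6-of-7 completion rule. None changes the number exposed to SHP639 in a cohort, which is 5.

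The point about consequence stands: the size is expressly not based on power, and no decision depends on the figure.

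**Conclusion.** The concern holds. The binomial arithmetic for 7 subjects is correct, but 7 is the wrong denominator for an AE rate in a dose group. For a standard cohort, the chance of seeing at least one occurrence among the SHP639 subjects is 55.6% at 15% incidence and 76.3% at 25%, about 9 points below each stated floor.

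This assumes independent subjects with a common incidence, and takes dose group to mean the SHP639 subjects of one cohort, which is how the AE tables are laid out. The error should be corrected, but it reaches no further than the justification: no enrolment number, analysis set, escalation rule or stopping rule changes.

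**What to change.** In Protocol 9.6, the synopsis and SAP 2.3, replace the sentence with:

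> With at least 5 subjects dosed with SHP639 per cohort, the probability of observing at least one occurrence of an AE with a true incidence of 15% to 25% is at least about 56% to 76%, respectively.

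Saying at least 5 covers replacements, who receive the same treatment as the subject they replace (Protocol 4.5), and enlarged or repeated cohorts. Saying dosed matches the safety set (Protocol 9.7, SAP 4.3) and removes the condition of 7 completers. It does apply one incidence to every dosed subject, including any who stop early and have less exposure.

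The change is one sentence in three places and a less favourable figure. Under Protocol 10.3.2 a protocol amendment needs sponsor and IRB approval, so the protocol wording could be carried in the next amendment made for other reasons.
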